**5.7.4 Procedural Exclusion**

During the procedure, the implanting investigator may determine transcatheter aortic valve implantation using the Portico TF or ALT Delivery System is neither feasible nor in the best interest of the subject. Any subject that does not have a delivery system enter his or her body will be withdrawn from the study. Data collected on these subjects, at baseline, will consist of reason(s) for exclusion and possible adverse events. Subjects that have a Delivery System enter his or her body but no valve will be followed for 30 days to collect adverse events.

Following the procedure, the delivery and loading systems should be securely disposed of per hospital requirements for hazardous materials. If there are any concerns noted with the delivery system, loading system, or valve during the procedure, they should be reported and returned to Abbott.

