#### 4.2 Study Design and Scope

This is a multicenter prospective, non-randomized, 2-arm investigational study without concurrent or matched controls, designed to assess the use of the Portico TF or Alternative Access Delivery System to place a Portico transcatheter aortic valve through an alternative access site, specifically subclavian/axillary or TAO.

A minimum of 45 subjects will undergo transcatheter aortic valve replacement (independent of valve size) via the Portico TF or Alternative Access Delivery System in each arm. A minimum of 45 implants will be accessed via the subclavian/axillary access site arm of the study and a minimum of 45 implants will be accessed via the TAO access site arm of the study. A maximum of 12 investigational sites with prior alternative access technique experience in Europe and will be trained to participate in the study. Enrollment is anticipated to be completed approximately 8 months from the date of first enrollment. Data will be collected at pre-procedure, peri-procedure and at discharge as well as at 30 days, 6 months and 1 year post implantation. All active subjects will be followed for 1 year.

Data from other prospective clinical trials of ALT access in similar patient populations outside of Europe may be included in the analysis and support the submission for CE Mark. CE Mark will be submitted for each access route after implantation and 30 day follow up are completed.

Although the study will not test a hypothesis, the primary endpoint event rate for each cohort will be presented within the context of the range of rates reported for alternative access delivery of transcatheter valves in the literature.

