##### 6.2.1.2 Analysis Population

All subjects who have received a Patient Information Sheet, and signed an Informed Consent Form and Data Protection Form will be considered enrolled in the study. However, the analysis population will be based on subjects who have provided signed Informed Consent Form and Data Protection Form and had the SJM TAVI delivery system enter his/her body. The anticipated dropout rate for this study population is expected to be low, as part of the selection criteria is subject compliance with all follow-up visits. Subjects that withdraw from the investigation or are lost to follow-up will not be replaced in the analysis dataset.

It is anticipated that there may be subjects who are enrolled in the study but are not included in the analysis population. There may be subjects who gave consent to participate in the study but did not satisfy the baseline inclusion exclusion criteria, these are considered screen failures. There may also be subjects who have enrolled in the study and started the procedure, but do not have the SJM TAVI delivery system enter his/her body and are procedural exclusions due to their anatomy, circumstances related to the procedure, or physician judgment; these are considered to be procedural exclusion subjects. Screen failure subjects and procedurally excluded subjects will not be part of the analysis population.

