### 6.2.2 Secondary Endpoints

The following endpoints will be summarized using descriptive statistics for each access arm of the study.

Event rates at 30 days for all-cause mortality, cardiovascular mortality, disabling stroke, non-disabling stroke, life threatening bleeding requiring transfusion, and acute kidney injury requiring dialysis and composite of periprocedural encephalopathy/all stroke/and all TIA:

The count and proportion of subjects who experience each of above endpoints as adjudicated by the CEC through 30 days post implant will be summarized. Subjects in the analysis population defined in section 6.2.1.2 will be included in the analysis.

Event rates at one year for all-cause mortality, cardiovascular mortality and disabling stroke:

Kaplan-Meier survival analysis will be used to estimate the event rates of all cause mortality, cardiovascular mortality and disabling stroke at one year post implant. Subjects in the analysis population defined in section 6.2.1.2 will be included in the analysis. The index procedure (TAVI) day is considered Day 0. The time-to-event will be determined from the date of index procedure to the first occurrence of the event for subjects experiencing the event, or, for those subjects not experiencing the event, to the last date they are known to be free of the event (this usually will be the last follow-up, contact date, or death date).

Rate of moderate or severe aortic regurgitation at one year:

The count and proportion of subjects with moderate or severe aortic regurgitation at one year will be summarized.

Functional improvements in NYHA classification, 6 minute walk test and EOA will be compared at 30 days:

Changes of NYHA classification, 6 minute walk and EOA at 30 days from baseline will be summarized using descriptive statistics.

Acute device success:

The count and proportion of subjects with acute device success (see Section 4.3.2) will be summarized.

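### Subjects with delivery system entry but no valve are in the 1-year Kaplan-Meier population but followed for only 30 days, so the 1-year mortality rates may be biased low

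*Combined protocol and SAP*

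**What the plan says.** Four statements in the protocol bear on this.

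- **Population (6.2.1.2).** The analysis population is consented subjects who "had the SJM TAVI delivery system enter his/her body". A valve implant is not required. The stated removals are narrow: "Screen failure subjects and procedurally excluded subjects will not be part of the analysis population". That section defines procedural exclusions as subjects in whom no delivery system entered, so a subject with entry but no valve stays in.
- **1-year estimator (6.2.2).** "Kaplan-Meier survival analysis will be used to estimate the event rates of all cause mortality, cardiovascular mortality and disabling stroke at one year post implant". On the population: "Subjects in the analysis population defined in section 6.2.1.2 will be included in the analysis". Subjects without the event are censored at the last date on which they are known to be free of it.
- **Follow-up after a failed implant (5.7.4).** "Subjects that have a Delivery System enter his or her body but no valve will be followed for 30 days to collect adverse events".
- **General follow-up (4.2, repeated in the synopsis).** "All active subjects will be followed for 1 year". Neither place defines active, so the reader cannot tell whether no-valve subjects count.

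Nothing else in the protocol closes the gap. Section 9.2 continues safety surveillance to the last visit but gives way where the plan specifies otherwise, and 5.7.4 does so. There is no later vital-status check for these subjects, no 1-year set restricted to implanted subjects, and no sensitivity analysis.

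**The concern.** Kaplan-Meier assumes that a censored subject has the same later risk as those still under observation. Here the censoring is triggered by failure to implant, not by chance or calendar time, and the subjects who remain observed are essentially those with a study valve. The estimator gives the censored subjects the valve recipients' hazard for the remaining 11 months.

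The plan's own background makes equal risk doubtful for mortality. Section 2.0 puts average life expectancy in severe symptomatic stenosis at 2-3 years from symptom onset and notes a risk of sudden death. Appendix D classifies sudden, unwitnessed and unexplained deaths as cardiovascular. Section 8.3 describes inoperable patients as being at increased risk of death, and section 8.2 lists conversion to open surgery among possible consequences, in subjects enrolled as high surgical risk. If later deaths in this group go unrecorded, the 1-year all-cause and cardiovascular mortality rates reported for each access route will be too low, and a confidence interval will not show it.

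**Working it through.** **No stated figure to reproduce.** The protocol gives no expected 1-year rate and no expected number of failed implants. What follows is an illustration.

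**Formula.** Let f be the share with no valve, s0 their 30-day survival, s1 the 30-day survival of valve recipients, and m0 and m1 the mortality from day 30 to 1 year without and with a valve.

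- Survival under full follow-up: (1 - f)·s1·(1 - m1) + f·s0·(1 - m0)
- Expected Kaplan-Meier survival with no-valve subjects censored at day 30: [(1 - f)·s1 + f·s0]·(1 - m1)
- Shortfall in the mortality estimate (the difference): f·s0·(m0 - m1)

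The shortfall is zero if f = 0 or m0 = m1.

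**Inputs.**

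- 45 subjects per arm: section 6.3.
- m0: take the 2-3 years of section 2.0 as an exponential mean (assumption) over the 335 days from day 30 to day 365, or 335/365 = 0.918 years. Mean 3 years: 1 - exp(-0.918/3) = 26.4%. Mean 2 years: 1 - exp(-0.918/2) = 36.8%.
- m1, s0 and the number of no-valve subjects are not in the documents. Set A assumes m1 = 10% and 30-day mortality of 5% in everyone (s0 = 0.95). Set B assumes m1 = 9% and 30-day mortality of 10% in no-valve subjects (s0 = 0.90). Both are run with 2 and 5 no-valve subjects.

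**Results (shortfall, percentage points).**

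| No valve | Set A | Set B |
|---|---|---|
| 2 of 45 | (2/45)·0.95·(0.264 - 0.10) = 0.7, to (2/45)·0.95·(0.368 - 0.10) = 1.1 | (2/45)·0.90·(0.264 - 0.09) = 0.7, to (2/45)·0.90·(0.368 - 0.09) = 1.1 |
| 5 of 45 | (5/45)·0.95·0.164 = 1.7, to (5/45)·0.95·0.268 = 2.8 | (5/45)·0.90·0.174 = 1.7, to (5/45)·0.90·0.278 = 2.8 |

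Under Set A the Kaplan-Meier rate is 1 - 0.95·0.90 = 14.5%. Full follow-up would give about 15.2-15.6% with 2 no-valve subjects and 16.2-17.3% with 5.

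**Outer case.** With 5 of 45 and m0 = 50%, a value with no source in the documents, the shortfall under Set A is (5/45)·0.95·0.40 = 4.2 points.

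**Scale.** The 95% sampling half-width for a 15% rate with n = 45 is 1.96·√(0.15·0.85/45) = 10.4 points. With 2 no-valve subjects, a shortfall of 0.7-1.1 points is 0.3-0.5 of one expected death per arm (45 × 0.007 to 45 × 0.011).

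**The case against.** The strongest reply accepts the mismatch and disputes its consequence.

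- **The bias is conditional.** It needs failed implants and a higher later hazard. Section 2.0 is natural history from symptom onset, not data on failed implants, and section 8.3 speaks of inoperable patients whereas this trial enrols subjects at high operable risk. Section 4.4 allows the route to reflect operator and patient preference, so a valve by another route is not ruled out; such subjects could have later risk close to that of valve recipients. This stands: the direction is plausible for mortality but not demonstrated.
- **Stroke.** A reader might infer that the disabling stroke rate is also biased low. The documents do not support that. The prognostic statements concern death, and section 6.2.2 also censors at death in the stroke analysis, which tends to push a Kaplan-Meier event rate up. What remains is a data gap: Appendix D grades disability by mRS at 90 days after the event, beyond the 30-day follow-up. Section 5.9 asks for a 90-day visit without excluding these subjects, but 5.7.4 is not reconciled with it.
- **Little depends on it.** Failed delivery is still recorded under acute device success. The 30-day endpoints, including the primary, count these subjects in full. The CE Mark analysis is locked on 30-day data (6.5), and the 1-year rates are descriptive with no threshold. This also stands. A reader who took the problem to undermine the primary safety result would be going beyond the documents.
- **Some later information may arrive anyway.** Section 5.15 follows withdrawals due to an adverse event until resolution or stability, and the 5.9 visit may capture others. These are partial safeguards that do not give systematic 1-year status.

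None of this removes the mismatch: the plan as written includes these subjects in a 1-year estimate and stops observing them at one month.

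**Conclusion.** The inconsistency between 5.7.4, 4.2, 6.2.1.2 and 6.2.2 is certain. Its effect on the estimates is not. The 1-year all-cause and cardiovascular mortality rates may be biased low. The illustration covers all-cause mortality only and rests on an exponential reading of 2-3 years and on assumed risks and failure counts. On that footing the effect is about 1 point with 2 no-valve subjects per arm and up to about 3 points with 5, small beside the sampling error. The tempting stronger statement, that the 1-year rates are biased low in favour of the device, is not supported without a count of failed implants and evidence on what happens to those subjects. The point still deserves correction, because successful delivery by these routes is what the study assesses and the remedy is cheap.

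**What to change.** Amend section 5.7.4 so that, for subjects with delivery system entry and no valve, data collection runs to 1 year for vital status, cause of death and stroke. Telephone or general practitioner contact at 6 months and 1 year is enough; no echocardiogram or walk test is needed. State in 6.2.2 that these data enter the 1-year analyses. Define active in 4.2 and the synopsis consistently with this, and say how the 90-day assessment in 5.9 applies to these subjects.

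If later status cannot be obtained, label the 1-year estimates as resting on day-30 censoring of no-valve subjects, report how many there are, and add a sensitivity analysis that varies their later mortality from equal to that of valve recipients upwards.

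The cost is a protocol amendment, a few contacts per arm, and possibly slightly less favourable 1-year rates.

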**5.8 Scheduled Follow-ups****5.8.1 Discharge Visit**

The discharge visit will take place at the time of hospital discharge or 7 days post implant, whichever occurs first. Discharge testing maybe completed the day after procedure up until discharge or within 7 days if the subject has yet to be discharged. The discharge assessment will include:

1. Physical assessment
2. Barthel Index
3. NIH Stroke Scale
4. Echocardiography (to be performed between 24 hours and 7 days post implant)
5. ECG
6. Blood work
7. Medication assessment
8. Adverse events assessment

**5.8.2 30-Day Visit**

The 30-Day visit window is 30-7/+14 days after the index procedure, and will include:

1. Physical assessment
2. Barthel Index
3. Modified Rankin Stroke Scale
4. NIH Stroke Scale

**Clinical Investigational Plan**

5. Echocardiography
6. ECG
7. Blood work
8. NYHA Functional Classification
9. Frailty Index assessment
10. Quality of Life Questionnaire (QOL)
11. Six Minute Walk Test
12. Medication assessment
13. Adverse events assessment

**5.8.3 6-Month Visit**

The 6-Month (180 days) visit window is 180±30 days after the index procedure and will include:

1. Physical assessment
2. Echocardiography
3. ECG
4. NYHA Functional Classification
5. Medication assessment
6. Adverse events assessment

**5.8.4 1 Year Visit**

The 1 year (360 days) visit window is 360±30 days after the index procedure and will include:

1. Physical assessment
2. Modified Rankin Stroke Scale
3. NIH Stroke Scale
4. Echocardiography
5. ECG
6. Barthel Index
7. Blood work
8. NYHA Functional Classification
9. Frailty Index assessment
10. Quality of Life Questionnaire (QoL)
11. Six Minute Walk Test
12. Medication assessment
13. Adverse events assessment

**5.9 Unscheduled Visit for Evaluation of Suspected Neurological Event**

If the subject experiences a neurological event (TIA, stroke, or encephalopathy), the event should be documented on an adverse event form and further evaluation should be performed at an unscheduled visit 90 days (±14 days) from the date of the neurological event. The unscheduled visit will include the following assessments:

1. Barthel Index
2. NIH Stroke Scale
3. Modified Rankin Stroke Scale

**5.10 Blood Work**

Subject's blood samples will be collected at the intervals indicated in Table 4

 FDA's Current Thinking Regarding Neurological Assessments for Transcatheter Valve Trials (Revised: August 25, 2011)

## Clinical Investigational Plan

**Table 4. Laboratory Scheme**

Lab Test	Baseline	Procedure		Discharge	30 days, & 1 Year
		Pre	Post		
Complete Blood Count 
 
White Blood Cell Count
 
Red Blood Cell Count
 
Hemoglobin
 
Hematocrit
 
	X			X	
Platelet count	X			X	
Urea and Creatinine	X	X*	X**	X	X
BNP or ProBNP	X			X	X
INR (if subject is on Coumadin/Warfarin)	X				
Troponin or CK, CK-MB	X				
Albumin	X				X

\* Within 72 hours before index procedure

\*\*Within 48 hours after index procedure

### 5.11 Imaging

Echocardiographic examinations will be conducted at the intervals indicated in Table 3 of this Clinical Investigation Plan. Each site is responsible for performing the echocardiogram according to the Echocardiographic Protocol.

Echocardiographic examinations will be forwarded to the Echocardiographic Core Laboratory for interpretation. It is the responsibility of each site to perform the local interpretation of the echocardiogram for clinical assessment.

The Echocardiographic Core Laboratory will not be responsible to notify the site of any abnormal findings that are identified in the echo study. The responsibility of the Echocardiographic Core Laboratory is to complete the echocardiography data collection forms and submit these to the Sponsor.

The Echocardiographic Core Laboratory will provide the study required interpretation and documentation of each echocardiogram submitted. Data obtained from the core laboratory readings will be used for study purposes only and not for clinical treatment of the subject. Abbott will use only the measurements from the Echocardiographic Core Laboratory for analysis. If the Core Laboratory determines the echocardiogram is unreadable, the site will be responsible for having the subject return for another echocardiogram.

### 5.12 Medications

The subject's use of the following medications will be collected at each visit:

## Clinical Investigational Plan

- Beta Blockers
- Calcium Channel Blockers
- Anticoagulants
- Antiplatelet agents including Aspirin
- Diuretics
- ACE Inhibitors
- Angiotensin Receptor Blockers (ARBs)

### 5.13 Description of Activities Performed by Sponsor Representatives

Trained Sponsor personnel may perform certain activities to ensure compliance to the clinical investigational plan and may provide technical expertise during the implant procedure.

### 5.14 Subject Study Completion

When the subject's participation in the clinical study has been completed the subject will return to the medical care as per physician's recommendation.

### 5.15 Subject Withdrawal

Subjects must be informed about their right to withdraw from the study at any time and for any reason without sanction, penalty or loss of benefits to which the subject is otherwise entitled and withdrawal from the study will not jeopardize their future medical care or relationship with the Investigator. Subjects will be asked to specify the reason for the termination, but have the right not to answer.

The Investigator may decide to withdraw a subject from the study at any time with reasonable rationale. The subject's future care will not be influenced by a decision, voluntary or otherwise, to withdraw from the study. All reasonable efforts should be made to retain the subject in the clinical study until completion of the study.

Reasons for subject's withdrawal include, but are not limited to:

1. Subject refuses to continue participating in the study
2. Subject does not have a delivery system enter his or her body
3. Subject does not meet the inclusion/exclusion criteria and does not require additional follow-up for safety reasons.
4. Subject is deceased (cause must be documented)
5. Subject's non-compliance
6. Subject's participation is terminated by the PI or Investigator, although the subject consented, since participation is no longer medically appropriate

Every effort will be made to obtain follow-up data. Potential methods of subject tracking should be documented and may include:

- Attempting to contact the subject by multiple phone calls and letters documented at the site
- Mailing a registered letter to the subject's last known address requesting that the subject contact the site

If a subject cannot be located after at least two documented contact attempts, the patient's general practitioner shall quickly be contacted to investigate about the subjects whereabouts and its health status.

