## Clinical Investigational Plan

Note: If a subject misses one or more of the scheduled follow up visits (inclusive of the assigned visit windows), this will be considered as a missed visit. The subject may therefore still return for subsequent visits and will not be excluded from the study.

If a subject withdraws from the clinical study, the site will record the subject's reasons for withdrawal, on a Withdrawal CRF.

When subject withdrawal from the clinical study is due to an adverse event the subject will be followed until resolution of that adverse event or determination that the subject's condition is stable. The status of the subject's condition should be documented at the time of withdrawal.

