#### 9.2 Safety Reporting

Safety surveillance and safety reporting for this study are both performed by the Investigator (per the local country requirements) and starts as soon as the subject is enrolled in this study (date of signature of the informed consent). German requirements are outlined in Appendix M. Safety surveillance and safety reporting will continue until the last investigational visit has been performed, the subject is deceased, the subject/investigator concludes his participation into the study or the subject/investigator withdraws the subject from the study, except as otherwise specified in the CIP.

All reportable adverse event data including deaths and device deficiency data will be collected throughout the clinical study and will be reported to the Sponsor through the EDC system. The Investigator will record all reportable adverse events and device deficiencies on the appropriate case report forms.

Records relating to the subject's subsequent medical course must be maintained and submitted (as applicable) to the Sponsor until the event has subsided or, in case of permanent impairment, until the event stabilizes and the overall clinical outcome has been ascertained. Adverse events will be monitored until they are adequately resolved, the subject is withdrawn, or completes the study. The status of the subject's condition should be documented at each visit.

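### Investigators may withdraw treated subjects under section 5.15, and nothing then requires vital or stroke status at 1 year, so the 1-year Kaplan-Meier estimates are open to informative censoring

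*Combined protocol and SAP*

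**What the plan says.** Section 5.15 gives a general power: "The Investigator may decide to withdraw a subject from the study at any time with reasonable rationale". Its list of reasons includes, as reason 5, "Subject's non-compliance" and, as reason 6, "Subject's participation is terminated by the PI or Investigator, although the subject consented, since participation is no longer medically appropriate". Neither is defined further or limited to the time before the procedure. Reason 2, by contrast, is expressly about subjects in whom no delivery system was introduced. Reason 3 carries a condition: "Subject does not meet the inclusion/exclusion criteria and does not require additional follow-up for safety reasons".

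Two later statements in 5.15 bear on who stays under observation. On missed visits: "The subject may therefore still return for subsequent visits and will not be excluded from the study". On withdrawal due to an adverse event: "the subject will be followed until resolution of that adverse event or determination that the subject's condition is stable".

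Section 9.2 lets safety surveillance end when the subject or investigator "withdraws the subject from the study, except as otherwise specified in the CIP". A separate sentence in 9.2 reads: "Adverse events will be monitored until they are adequately resolved, the subject is withdrawn, or completes the study".

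Section 4.2 commits to 1 year of follow-up for active subjects. Section 6.2.2 estimates 1-year all-cause mortality, cardiovascular mortality and disabling stroke by Kaplan-Meier, censoring event-free subjects at the last date they were known to be event-free. Section 6.2.1.2 says that withdrawn subjects are not replaced and that dropout should be low, without a figure. No sensitivity analysis for withdrawals is planned.

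**The concern.** The treatment is a single implant. Once it is done, withdrawal can end only observation, and what is then lost is outcome data on a subject who remains in the analysis population.

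Reason 6 turns on the subject's medical condition, so it is plausibly related to prognosis. Kaplan-Meier estimation treats a censored subject as having the same later risk as those who remain. If investigators tend to withdraw subjects who are doing badly, deaths and strokes after withdrawal go uncounted and the 1-year estimates are too low. In an uncontrolled study with 45 subjects per arm, a few such subjects would visibly change the reported rate.

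The text also leaves sites unsure what to do. Section 5.15 follows an adverse event after a withdrawal that the event caused, whereas the monitoring sentence in 9.2 ends at withdrawal. The relation between a missed visit and non-compliance is not spelled out.

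**Working it through.** **Plan figures.** The documents give no withdrawal rate and no expected 1-year mortality. The only precision figure, in section 6.3, is the exact 90% interval of 1.45% to 15.32% for a 5.9% rate in 45 subjects. Clopper-Pearson limits with 0.059 × 45 = 2.655 events reproduce it (1.452%, 15.322%). It concerns the 30-day primary endpoint and is not used below.

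**Step 1: follow one subject through the text.** Suppose a treated subject is withdrawn under reason 6 some months after the implant, and the stated reason is not an adverse event.

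- 5.15 permits it, because the power applies at any time.
- 9.2 ends surveillance by default. The clause deferring to other parts of the plan does not help, because the 5.15 exception covers only withdrawals due to an adverse event.
- If the withdrawal was due to an adverse event, follow-up continues, but only to resolution or stability.
- 4.2 no longer applies, because the subject is not active.
- General practitioner contact in 5.15 is triggered when a subject cannot be located. This subject is not lost.
- 6.2.2 censors the subject at the last event-free date.

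No step obtains vital or stroke status at 1 year.

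**Step 2: worst case (assumed counts).** Take n = 45 (section 6.3), D true deaths by 1 year, and w of those subjects withdrawn alive whose deaths are never seen. There is no other censoring. If they are censored before any observed death, the Kaplan-Meier estimate is (D − w)/(45 − w). If they are censored after all observed deaths, it is (D − w)/45.

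| True deaths D | True rate | w = 1 | w = 2 | w = 3 |
|---|---|---|---|---|
| 5 | 11.1% | 8.9–9.1% | 6.7–7.0% | 4.4–4.8% |
| 7 | 15.6% | 13.3–13.6% | 11.1–11.6% | 8.9–9.5% |
| 9 | 20.0% | 17.8–18.2% | 15.6–16.3% | 13.3–14.3% |

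For D = 7 and w = 2, for example: 5/43 = 11.6% and 5/45 = 11.1%. Under late censoring each unseen death costs 1/45 = 2.2 points. The smallest loss in the table is 20.0 − 18.2 = 1.8 points.

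**Step 3: milder case (assumed counts).** Assume 2 deaths by day 30 and 4 later observed deaths. A further k subjects are withdrawn soon after day 30, of whom d die unseen. The Kaplan-Meier estimate is 1 − (1 − 2/45) × (1 − 4/(43 − k)), and the true rate is (6 + d)/45.

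| k | d | Kaplan-Meier | True | Gap (points) |
|---|---|---|---|---|
| 2 | 1 | 1 − (43/45)(37/41) = 13.8% | 7/45 = 15.6% | 1.8 |
| 3 | 2 | 1 − (43/45)(36/40) = 14.0% | 8/45 = 17.8% | 3.8 |
| 4 | 3 | 1 − (43/45)(35/39) = 14.2% | 9/45 = 20.0% | 5.8 |

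The gap per unseen death is again just under 2 points. These rows assume that 50%, 67% and 75% of withdrawn subjects die, against about 10% of those who stay (4/41, 4/40, 4/39). If withdrawal is unrelated to prognosis, there is no systematic bias.

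**The case against.** The plan has real safeguards.

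- **Surveillance.** A reader might infer that it stops outright at withdrawal. The text does not support that. 9.2 defers to the rest of the plan, 5.15 continues follow-up for withdrawals due to an adverse event, and 9.2 also asks for records of the later medical course until an event subsides or stabilises. These provisions are tied to individual events, however, and end before they would secure 1-year status.
- **Ineligibility.** A reader might count late-found ineligibility as another route out. Reason 3 applies only where no safety follow-up is needed, and section 7.2 places eligibility review before implant. Nothing shows that it is aimed at treated subjects.
- **Missed visits.** A reader might see a flat contradiction between the missed-visit note and reason 5. Non-compliance is a wider term than a missed visit, and section 9.1 treats a missed visit, or being too ill for a test, as a deviation. A frail subject who cannot attend should therefore stay in the study. What remains is an ambiguity.
- **Selective loss.** A reader might conclude that follow-up does end selectively in deteriorating subjects. That is a risk, not something the documents establish. Dropout is expected to be low, 5.15 asks for reasonable efforts at retention, and it follows the withdrawal list with a commitment to seek follow-up data. The methods it names, though, are for tracing subjects who have gone missing.
- **Size.** The counts above are chosen. One unseen death is small beside sampling error: the exact 95% interval for 7/45 runs from 6.5% to 29.5%. The affected outcomes are secondary and descriptive. The primary endpoint is at 30 days, and the CE Mark dataset is locked after the 30-day visits (section 6.5).

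These points limit the size and certainty of the problem. None of them supplies a requirement for 1-year status after an investigator's withdrawal.

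**Conclusion.** The point holds as a gap in required follow-up. Investigators may withdraw treated subjects under reasons 5 and 6, surveillance then ends by default with one limited exception, and the 1-year Kaplan-Meier estimates have no protection against prognosis-related censoring. The likely direction is towards a rate that is too low.

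The size is about 2 percentage points of 1-year mortality per unseen death in an arm of 45 (1.8 to 2.2 across the worked cases). This depends on assumed counts and on withdrawal being related to prognosis. The interval around the estimate would not reflect this bias. The same mechanism applies to cardiovascular mortality and disabling stroke, but the documents give no basis for a figure.

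The plan should be changed here, although the matter does not threaten the 30-day primary endpoint. The adverse event follow-up passages in 5.15 and 9.2 must be reconciled in any case.

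**What to change.** In 5.15, state that once the delivery system has entered the body, investigator-initiated withdrawal under reasons 5 and 6 stops study visits only. Unless the subject withdraws consent, collect vital status, stroke and serious events to 1 year by phone or through the general practitioner. For subjects with no valve implanted, collect them to 30 days, matching section 5.7.4. When consent is withdrawn, ask whether vital status may still be collected. Make clear that missed visits alone are not non-compliance.

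Reconcile the 9.2 sentence that ends adverse event monitoring at withdrawal with the 5.15 provision for withdrawals due to an adverse event.

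In 6.2.2, report the 1-year Kaplan-Meier estimates with a worst-case or tipping-point analysis for withdrawn subjects.

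The cost is protocol and consent wording plus a few contacts per withdrawn subject. Two limits remain. Remote follow-up will not recover the 1-year echocardiogram, and classifying a stroke as disabling still needs the 90-day modified Rankin score from a certified rater.
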